7.1.3 Study medication permanent discontinuation criteria

Study participants **must** permanently discontinue study medication if any of the following events occur:

- 1. Study participant develops an illness that would interfere with his or her continued participation.
- 2a. Study participant has new onset or reoccurrence of malignant neoplastic disease (except for superficial basal or squamous cell carcinoma of the skin not requiring targeted biological therapy, chemotherapy or radiation).3. Study participant experiences an infective episode including but not limited to bacteremia or sepsis, infectious meningitis, septic arthritis, osteomyelitis, complicated pneumonia, or visceral abscess, which may or may not result in hospitalization during a Treatment Period (Appendix 13 [Section 10.13.2]). This list is not intended to be all inclusive, and the investigator is expected to apply their judgment on continuing IMP based on the clinical situation.
- 4. Study participant meets PDILI permanent discontinuation criteria.
- 5. Study participant has a TB test that is confirmed positive or any further evidence suggestive of potential TB infection (ie, exposure) and further examinations result in a diagnosis of active TB or LTBI.
- 6. If a NTMBI is identified during a study, the same withdrawal procedures as those used for an active TB infection identified during the study should be followed.

- 7. Study participant has an AE of severe or serious infusion-related reaction, hypersensitivity, or anaphylactic reaction requiring corticosteroid and/or epinephrine therapy (Sampson et al, 2006; Appendix 13 [Section 10.13.1]).
- 8. Study participant takes prohibited concomitant medications as defined in this protocol.
- 9. Study participant has a recurrence of aseptic meningitis (see also Appendix 14 [Section 10.14]).
- 10. Study participant has as indicated by a positive response (Yes) to either Question 4 or Question 5 of the "Since Last Visit" version of the C-SSRS. The study participants should be referred immediately to a mental healthcare professional.

Study participants **may** permanently discontinue rozanolixizumab at the discretion of the investigator (following consultation with the sponsor's medical monitor or study physician if necessary) if the study participant is noncompliant or becomes unable to comply with the study procedures or medications in the opinion of the investigator.

Investigators should contact the medical monitor, whenever possible, to discuss the withdrawal of a participant in advance. Investigators should attempt to obtain information on study participants in the event of withdrawal (eg, reason for withdrawal, any safety information).

Study participants who permanently discontinue study medication should undergo an Early Withdrawal Visit and move into the Safety Follow-up Period. Handling of replacement participants is described in Section 7.2.

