- When an AE/SAE occurs, it is the responsibility of the investigator to review all
 documentation (eg, hospital progress notes, laboratory reports, and diagnostics reports) related
 to the event.
- The investigator will then record all relevant AE/SAE information in the CRF.
- It is **not** acceptable for the investigator to send photocopies of the participant's medical records to UCB in lieu of completion of the UCB AE/SAE CRF page.
- There may be instances when copies of medical records for certain cases are requested by
 UCB. In this case, all participant identifiers, with the exception of the participant number, will
 be redacted on the copies of the medical records before submission to UCB.
- The investigator will attempt to establish a diagnosis of the event based on signs, symptoms, and/or other clinical information. Whenever possible, the diagnosis (not the individual signs/symptoms) will be documented as the AE/SAE.

Assessment of intensity

The investigator will make an assessment of intensity for each AE and SAE reported during the study and assign it to 1 of the following categories:

- Mild: An event that is easily tolerated by the participant, causing minimal discomfort and not interfering with everyday activities.
- Moderate: An event that causes sufficient discomfort and interferes with normal everyday activities.
- Severe: An event that prevents normal everyday activities. An AE that is assessed as severe should not be confused with a SAE. Severe is a category utilized for rating the intensity of an event; and both AEs and SAEs can be assessed as severe.
- An event is defined as 'serious' when it meets at least 1 of the predefined outcomes as described in the definition of a SAE, NOT when it is rated as severe (eg, a severe AE may be either serious or not serious, depending on whether these criteria are also met).

The National Cancer Institute Common Terminology Criteria for Adverse Events (NCI-CTCAE) should be used as a supportive standardization instrument to evaluate AEs and SAEs but the final intensity grading by the investigator must be mild, moderate, or severe.

Assessment of causality

- The investigator is obligated to assess the relationship between study medication and each occurrence of each AE/SAE.
- A "reasonable possibility" of a relationship conveys that there are facts, evidence, and/or arguments to suggest a causal relationship, rather than a relationship cannot be ruled out.

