10.13.1 Management of infusion reactions or hypersensitivity reactions

Study participants must be closely monitored for reactions during and after rozanolixizumab administration. Standard precautions must be taken for the study participants with regard to potential infusion-related reactions. Suggested management guidelines for infusion-related reactions and anaphylaxis at the study site are provided in Table 10-4. Definitions of the severity of the relevant events will be consistent with NCI-CTCAE version 5.0 (Appendix 3 [Section 10.3]). It is recommended that for study participants who self-administer at home, consideration is given to readily-available emergency medical services in case of an infusion reaction or hypersensitivity reaction. During study drug administration, the participant's home or alternative location must not be so remote that a reasonable arrival time of an ambulance could not be predicted.

Table 10-4: Suggested management guidelines at the study site for infusion reactions

| Type of r | eaction Sugges | sted action |
|------------|----------------|--|
| Acute – M | Iild Monito | or vital signs every 10 minutes. |
| Grade 1 | If the r | eaction worsens to Grade 2, follow the instructions below. |
| | | B/ 5/1,013 |
| Acute – M | | pt/hold infusion temporarily to further assess and initiate |
| Grade 2 | | ent if necessary. |
| | | er the use of IV fluid and antihistamine IV or IM. |
| | | er administering paracetamol or nonsteroidal anti-inflammatory |
| | drugs. | |
| | Monito | or vital signs initially every 5 minutes. |
| | | eaction improves and upon further assessment it is clear that the |
| | | s not an anaphylaxis, restart the infusion cautiously. Continue to |
| | | r vital signs every 5 minutes. |
| | If react | cion recurs or worsens to Grade 3, discontinue infusion. |
| This docum | S. IICO | |
| 900 | OK, | |
| This | | |

Table 10-4: Suggested management guidelines at the study site for infusion reactions

| Acute – Severe | Discontinue rozanolixizumab infusion permanently. |
|----------------|--|
| Grade 3 or | Alert crash team. |
| anaphylaxis | Maintain airway; ensure oxygen is available. |
| | Administer: |
| | Antihistamine IV/IM, corticosteroids IV, epinephrine IM, and IV fluids as appropriate. |
| | Monitor vital signs every 2 minutes. |
| | Hospitalize, if condition not improving or worsens |
| | Monitor study participant until symptoms resolve. |

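### Section 7.1.3 criterion 7 and Table 10-4, which it cites, set different triggers for permanent discontinuation after an infusion or hypersensitivity reaction, and neither is said to prevail

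*Protocol*

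**What the plan says.** Protocol 7.1.3 lists events after which participants must "permanently discontinue study medication if any of the following events occur". Criterion 7 on that list reads: "Study participant has an AE of severe or serious infusion-related reaction, hypersensitivity, or anaphylactic reaction requiring corticosteroid and/or epinephrine therapy". It refers the reader to Appendix 13, section 10.13.1.

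Section 10.13.1 contains Table 10-4, which is headed as suggested management at the study site and is organised by grade.

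- **Grade 3 or anaphylaxis:** "Discontinue rozanolixizumab infusion permanently". The row sets no condition on seriousness or on the treatment needed. Corticosteroid and epinephrine appear in it only as treatments to give: "Antihistamine IV/IM, corticosteroids IV, epinephrine IM, and IV fluids as appropriate".
- **Grade 2:** hold the infusion, assess and treat. If the reaction improves and is clearly "not an anaphylaxis, restart the infusion cautiously". If it recurs or worsens to Grade 3, the infusion is discontinued; here the table does not add that the stop is permanent.

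Protocol 8.3.8 directs that suspected reactions of this kind be managed by the Appendix 13 guidance, so the table is part of what sites are told to follow.

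**The concern.** Criterion 7 sends the reader to a section that applies a different test. The criterion turns on severity or seriousness, joined to a need for corticosteroid or epinephrine. The table turns on grade or anaphylaxis alone. A site that follows the cross-reference cannot tell from the text which test decides whether a participant stops study medication for good.

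This is an acute-safety stopping rule in a study where participants go on to infuse at home without a health care professional present. For a reaction at Visit 9, the planned infusions still to come are Visits 10 to 19, which is 10 doses. Six of these are at home (Visits 10 to 12 and 16 to 18; SAP 1.2 and 4.4.6). The same decision determines whether an event is counted as a TEAE leading to permanent withdrawal, an other endpoint tabulated by self-administration method (protocol 9.3.3, SAP 4.4.7). If sites settle the ambiguity differently, that count is not uniform across sites.

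**Working it through.** There is no stated figure to reproduce; the check is a comparison of two decision rules.

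**Inputs.** Criterion 7 in protocol 7.1.3; the Grade 2 and Grade 3/anaphylaxis rows of Table 10-4 in 10.13.1. Appendix 3 (10.3) states that severity and seriousness are separate attributes, so each can occur without the other.

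**Two readings of criterion 7.** The sentence can be parsed in at least two ways:

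- Reading A: the need for corticosteroid or epinephrine applies to all three reaction types.
- Reading B: it applies to anaphylactic reaction only, so a severe or serious infusion-related or hypersensitivity reaction is enough by itself.

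**Side by side.** Permanently in the table is taken here to mean study medication; the other meaning is treated below. A drug that was given is taken as having been required.

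| Reaction | Table 10-4 | Criterion 7, reading A | Criterion 7, reading B |
|---|---|---|---|
| Grade 3, not anaphylaxis, corticosteroid or epinephrine needed | permanent stop | mandatory stop | mandatory stop |
| Grade 3, not anaphylaxis, neither drug needed | permanent stop | no mandatory stop | mandatory stop |
| Anaphylaxis, neither drug needed | permanent stop | no mandatory stop | no mandatory stop |
| Grade 2, serious, not anaphylaxis, corticosteroid given | restart allowed after improvement | mandatory stop | mandatory stop |

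The first row agrees throughout. The second differs under reading A only. The third differs under both readings but is a logical case that may seldom arise. The fourth differs under both readings, because the Grade 2 row has no exception for a serious event.

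**Full grid.** Crossing grade (1, 2, 3), serious (yes/no), anaphylaxis (yes/no) and drug needed (yes/no) gives 3 × 2 × 2 × 2 = 24 combinations. The two texts differ on permanent stop in 12 of 24 under reading A and 10 of 24 under reading B. These count logical combinations, some of them clinically unlikely. They show that the mismatch does not depend on one reading; they are not event frequencies.

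**Meaning of permanently.** The table speaks of the infusion and 7.1.3 of study medication. If the table means only the infusion in progress, the difference in the second and third rows disappears, but the table then says nothing about later doses. The Grade 2 row orders discontinuation without the word permanently, which suggests that the word adds something in the Grade 3 row. The text does not settle it.

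**The case against.** The strongest reply is that the two texts do different jobs. Section 7.1.3 is a mandatory list about study medication; Table 10-4 is suggested bedside guidance during a reaction at the site. In the Grade 3 case, criterion 7 only fails to require a stop. It does not authorise further dosing, and a site that follows the table breaches nothing in 7.1.3. This stands, and it limits the point. It does not remove it: no precedence is stated, and letting 7.1.3 prevail would settle only the Grade 2 case, since in the Grade 3 and anaphylaxis cases the table is the stricter text.

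The Grade 2 mismatch is narrow. That row does not list corticosteroid among its treatments, and seriousness may be recognised only after the infusion has restarted, in which case the two steps are sequential.

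There are also safeguards. Section 7.1.2 allows the investigator to hold dosing and calls for discussion with the medical monitor or study physician before it resumes. Section 7.2 allows withdrawal from the study for safety. Section 8 requires immediate safety concerns to be taken to the sponsor. These limit the risk but do not set a uniform rule. The discretionary clause in 7.1.3 itself covers only noncompliance or inability to comply.

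Three stronger inferences are tempting, and the documents do not support them:

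- *Sites may take opposite actions on the same event.* For Grade 3 the contrast is between a stop and the absence of a mandatory stop, not between a stop and permission to continue.
- *A Grade 2 reaction with an overnight stay but no corticosteroid must stop.* This needs reading B, while the Grade 3 example needs reading A; the two cannot be held together.
- *The severity scales conflict.* Appendix 13 says "Definitions of the severity of the relevant events will be consistent with NCI-CTCAE version 5.0" and Appendix 3 says "the final intensity grading by the investigator must be mild, moderate, or severe". But Table 10-4 pairs mild, moderate and severe with Grades 1, 2 and 3, the Appendix 13 sentence refers to Appendix 3, and Appendix 3 uses CTCAE as its supporting standard. That largely answers the point.

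**Conclusion.** The point holds in a limited form. Criterion 7 and the table it cites state different triggers for permanent discontinuation, and the protocol does not say which governs. The Grade 3 mismatch rests on reading A and on permanently meaning study medication. The Grade 2 mismatch holds under either reading but is confined to a serious reaction for which corticosteroid was given. Two ambiguities stand by themselves: which reaction types the treatment condition covers, and what the table's permanent stop refers to.

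The size cannot be given, because the documents state no frequency for these reactions. For a single event the wording bears on whether a stop is mandatory with up to 10 planned doses remaining after Visit 9; discretion and sponsor consultation may lead to the same decision under either text. The count of TEAEs leading to permanent withdrawal is summarised without a confidence interval (SAP 4.8).

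A reader might infer that the primary result is at risk, because the Full Analysis Set requires self-administration at Visits 13 and 19. A permanent stop before Visit 19 would remove the participant from that set. The effect is secondary and cannot be quantified from the documents, and the SAP repeats the primary analysis on the Randomized Safety Set (4.2.3).

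**What to change.** Reconcile criterion 7 in 7.1.3 with Table 10-4 in 10.13.1:

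1. Use one trigger for permanent discontinuation in both places, including how a serious Grade 2 reaction is handled.
2. State which of the three reaction types the corticosteroid or epinephrine condition covers.
3. State whether permanently in the table refers to the infusion in progress or to study medication.
4. State which text prevails if they still differ.

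Which rule to adopt is for the sponsor to decide. The cost is wording in two places and a memo to sites; no procedure, visit or data item is added.

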7.2 Participant discontinuation/withdrawal from the study

Participants are free to withdraw from the study at any time, without prejudice to their continued care.

Study participants **must** be withdrawn from the study if any of the following events occur:

- 1. Study participant withdraws his/her consent.
- 2. The sponsor or a regulatory agency requests withdrawal of the study participant.
- 3. There is confirmation of a pregnancy during the study, as evidenced by a positive pregnancy test

A participant **may** withdraw from the study at any time at his/her own request, or may be withdrawn at any time at the discretion of the investigator for safety, behavioral, compliance, or administrative reasons.

If study participants discontinue before the end of the Self-administration Period 2, replacement participants may be considered at the discretion of the sponsor, depending on how the discontinuation affects the study's ability to collect sufficient data to support the study objectives. For each case of participant discontinuation, the decision on whether to recruit a replacement and the reason behind the decision will be documented.

If the study participant withdraws consent for disclosure of future information, the sponsor may retain and continue to use any data collected before such a withdrawal of consent.

If a study participant withdraws from the study, he/she may request destruction of any samples taken and not tested, and the investigator must document this in the site study records.

See the Schedule of Activities in Section 1.3 for data to be collected at the Early Withdrawal Visit and for any further evaluations that need to be completed. In all cases except for withdrawal of consent, the study participant should also return to the site for an End of Study Visit.

Lost to follow-up

A participant will be considered lost to follow-up if he or she repeatedly fails to return for scheduled visits and is unable to be contacted by the study site.

The following actions must be taken if a participant fails to study visit:

- The site must attempt to contact the participant and reschedule the missed visit as soon as possible and counsel the participant on the importance of maintaining the assigned visit schedule and ascertain whether or not the participant wishes to and/or should continue in the study.
- Before a participant is deemed lost to follow-up, the investigator or designee must make every effort to regain contact with the participant (at least 1 phone call and 1 written message to the participant) and document his/her effort (date and summary of the phone call and copy of the written message in the source documents), to complete the final evaluation. All results of these evaluations and observations, together with a narrative description of the reason(s) for removing the participant, must be recorded in the source documents. The CRF must document the primary reason for withdrawal.

Should the participant continue to be unreachable, he or she will be considered to have withdrawn from the study with a primary reason of lost to follow-up documented in the CRF.

STUDY ASSESSMENTS AND PROCEDURES 8

Study procedures and their timing are summarized in the Schedule of Activities (Section 1.3). Protocol waivers or exemptions are not allowed.

Immediate safety concerns should be discussed with the sponsor immediately upon occurrence or awareness to determine if the participant should continue or discontinue study treatment.

Adherence to the study design requirements, including those specified in the Schedule of Activities, is essential and required for study conduct.

All screening evaluations must be completed and reviewed to confirm that potential participants meet all eligibility criteria. The investigator will maintain a screening log to record details of all participants screened and to confirm eligibility or record reasons for screening failure, as applicable.

Procedures conducted as part of the participant's routine clinical management (eg, blood count) and obtained before signing of the ICF may be utilized for screening or baseline purposes provided the procedures met the protocol-specified criteria and were performed within 4 weeks of the assessment timepoint in the Schedule of Activities.

An Unscheduled Visit can be conducted at the discretion of the investigator (eg, due to an AE) (see Section 4.1.1).

During the Unscheduled Visit, the following assessments will be performed:

- AE reporting
- Concomitant medications
- Review of withdrawal criteria
- Physical examination
- Vital signs

Blood samples for PK, IgG, hematology, biochemistry, and other laboratory testing and assessments may be performed as clinically indicated at the discretion of the investigator.

Repeat or unscheduled samples may be taken for safety reasons or for technical issues with the samples.

The maximum amount of blood collected from each participant over the duration of the study, including any extra assessments that may be required, will not exceed 500mL.

Some study-specific investigations may not be conducted according to the study protocol during a pandemic or other exceptional circumstances (eg, hurricanes) due to the need to implement safety measures and guidance from regulatory authorities. In such a situation, which may be accompanied by local or global containment or other measures, sites may need to prohibit access to study participants and study-related personnel. Study participants visits to the study site may be replaced by contingency measures. These measures are primarily established to ensure the safety of study participants during the course of the study and to maintain the study participants treatment schedule, if the investigator considers it appropriate. These measures include but are not limited to virtual visits or home-nursing visits replacing site visits, eg, telemedicine contacts or home-nursing visits when treatment and/or blood sampling is scheduled. The contingency measures are described in a contingency plan and will be implemented as required.

8.1 Efficacy assessments

Not applicable.

8.2 Safety assessments

Planned time points for all safety assessments are provided in the Schedule of Activities (Section 1.3).

8.2.1 Safe and successful self-administration

Safe and successful self-administration as defined in the endpoints (Section 3) will be evaluated at the site by the HCP supervising the self-administration process and via a mandatory direct contact with the study participant via telephone or video call as soon as possible after each home self-administration. The direct telephone or video contact with the study participant will also be used to document the study participant's self-assessment on the process of home self-administration, eg, on potential challenges and deficiencies.

Confidential

[figure not shown]
The HCP evaluation materials supporting the collection of data for Visit 13 (relating to primary endpoints are provided in Appendix 15 (Section 10.15).

8.2.2 Participant's preferred method of rozanolixizumab administration questions

me study participants will be asked to evaluate their relative preference for SC infusions performed by an HCP versus self-administration and the preference for the manual push method versus the use of a syringe driver for self-administration.

Materials supporting the collection of data relating to the participant's preferred method of rozanolixizumab administration are provided in Appendix 16 (Section 10 16)

Self-Injection Assessment Questionnaire (Infusion version) 8.2.3

Myasthenia Gravis Activities of Daily Living

The MG-ADL is an 8-item PRO instrument developed on the basis of the QMG (Wolfe et al, 1999). The MG-ADL targets symptoms and disability across ocular, bulbar, respiratory, and axial symptoms. In a recent study, reliability, validity, and responsiveness of the MG-ADL were further assessed. The questionnaire showed strong construct validity when evaluated against the MG-C as well as against the MG-QOL15r; high test-retest reliability in a 1-week interval; and it was demonstrated that a 2-point improvement indicates clinical improvement (Muppidi, 2012; Muppidi et al, 2011). The total MG-ADL score ranges from 0 to 24, with a higher score indicating more disability (Appendix 17 [Section 10.17]).

Confidential Page 48 of 124 The MG-ADL is being utilized in MG0020 as a parameter of symptom monitoring rather than an assessment of treatment benefit.

Independently of study visit type (site, home, or virtual), the MG-ADL must be completed by study participants in a quiet place by themselves without the help of a partner or caregiver, before any clinical examination takes place. Study participants should be informed of the importance of this questionnaire and instructed to read the items and instructions carefully. They should be informed that there are no correct or incorrect answers.

Study personnel are not allowed to interpret the items for the participant. If a participant asks for guidance, study personnel should instruct him or her to respond according to their best understanding of the item. The MG-ADL should only be checked for completeness by study personnel. In the event a few questionnaire items have not been completed, study personnel should only query this with the study participant, if this results from an omission. Study personnel shall neither complete missing data, nor suggest changes to participant responses. As with other study data, responses to the questionnaire should be treated as confidential information. Data privacy considerations apply.

